5.3 Informed Consent

Consent forms describing in detail the study intervention, study procedures, and risks are given to the participant and written documentation of informed consent is required prior to starting intervention/administering study intervention. Study information will be provided via online survey for clinicians and study consent will be provided over the phone for parents.

The following consent materials are submitted with this protocol:

- Clinician Information Form
- Parent Consent form

5.2.1 Screening (if applicable)

Not applicable.

5.2.2 Recruitment, Enrollment and Retention (if applicable)

5.3.3 Clinician Participants

Clinicians (N=50) who provide psychosocial interventions to K-12 students in our identified districts will be informed of the project using the following steps:

1. Clinicians receive an email from their supervisor (e.g., a “site leader” which could be a district or community mental health agency administrator, depending on whether

they are school- or community-employed) that the FOCUSS study team will contact them directly about participation. See “Clinician Notice of FOCUSS Study Email from Site Leader”. This will include “FOCUSS Flyer – Clinician”.

2. Site leaders will send the study team a list of names and email addresses of eligible clinicians.
3. Study team members will email clinicians directly with the “FOCUSS Flyer – Clinician” form attached. The email message will remind clinicians about the project and include a link to the first online survey. See “Qualtrics Invitation Email from Study Team – Clinicians”
4. Clinicians can view the Clinician Information Sheet and FOCUSS Flyer-Clinician on the first page of the online Qualtrics survey and provide contact information for the study team for any questions or clarifications they may have.
5. Two (2) reminders will be sent to clinicians who do not open the survey link. All clinicians will receive emails about the 3 month, 6 month, and 9 month surveys regardless of baseline survey completion. All follow-up surveys will include a link to the Clinician Information Sheet and FOCUSS Flyer-Clinician on the first page, as a reminder, and for any clinicians completing a follow-up survey as their first survey.

Parent/Guardian Participants

Consent will be collected over the phone for parents. Parent/guardians (N=150) who have a child receiving school-based mental health treatment from one of the participating clinicians will be recruited and consented using the following steps:

1. The clinician and/or designated site clinical staff will ask the parent/guardian of each recruited student if they are willing to be contacted by the study team. They will do this using the “Clinician Parent/Guardian Recruitment Script”.
2. If so, the parent’s contact information will be shared with relevant study team member using the “Research Interest Sheet – FOCUSS”, who will contact the parent via phone and/or email and then introduce the study, read the consent form, and request informed consent over the phone.
3. The study team member will indicate the parent’s consent (yes or no), and if yes, document the parent’s name, relationship to child, date, and their name and signature.

Study Visits (if applicable)

We will conduct study phone calls with parents at baseline, 3 months, 6 months, and 9 months. Each phone call will last approximately 20-25 minutes. Parents will be asked to provide ratings over the phone about their engagement in their child’s mental health services and their child’s mental health symptoms.

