4.1.1 General Design Description

A clustered, multiple-baseline design will be used to examine the impact of the implementation support condition on clinicians' fidelity, use and ratings of MBC appropriateness, acceptability and fidelity. Approximately 50 SMH clinicians will be recruited to participate from two school districts. All clinicians will receive the same implementation supports; there is no random assignment to condition. Following an initial control period of at least 1 month, school districts will start receiving implementation supports. During the initial control period, baseline MBC use, attitudes, acceptability, feasibility and appropriateness (per clinician self-report) will be collected, as well as needs assessment data from clinician surveys to inform necessary adjustments to the implementation supports. Baseline engagement and student outcomes will be collected after initial clinician training session. MBC implementation outcomes (i.e., MBC use, attitudes, acceptability, appropriateness, and feasibility), engagement and student outcomes will be collected at 3-month and 6-month follow-up during intervention supports, plus a 9-month follow-up interval. This allows clinicians in the two school districts to be compared to each other and to their own baseline. The primary comparison is pre-post ratings of implementation outcomes for all N=50 clinicians. The secondary comparisons are pre-post ratings of engagement and student outcomes, and between-agency differences.

Study Date Range and Duration

This study is expected to last approximately one calendar year from recruitment to follow-up, aligned with the 2021-2022 and 2022-23 academic years as the participating sites are school districts. Clinicians will start training and consultation in the fall of 2021 or 2022 and parents/guardians will be recruited in the fall of 2021 or 2022. Data collection will occur at baseline, 3 months, 6 months and 9 months.

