4.2 Outcome Variables

4.2.1 Primary Outcome Variables

The primary objective of this study is to examine implementation outcomes. Implementation outcomes are selected from a published taxonomy of outcomes include acceptability, appropriateness, feasibility and fidelity. **Acceptability, appropriateness, and feasibility** will be measured by clinician self-report on the Acceptability of Intervention Measure (AIM), Intervention Appropriateness Measure (IAM), and Feasibility of Intervention Measure (FIM) via web-based, clinician-report survey. These 4-item measures were developed based on input from 36 implementation scientists and 27 mental health professionals; structural validity, test-retest reliability, and sensitivity to change have been established. **MBC use (fidelity)** will be evaluated by chart review for evidence of two progress monitoring measures, the Session Rating Scale 3.0 (SRS) and Outcomes Rating Scale 3.0 (ORS). The ORS should be completed before each session to assess prior-week functioning, and the SRS will be completed at the end of the session to assess student/parent perceptions of alliance with the clinician. These will be stored in the Better Outcomes Now (BON) secure online system.

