5.2 Study Schedule

Clinician involvement will require approximately 9 hours of project activities during the 2021-22 or 2022-23 school year. All activities are part of their routine services and district-approved professional development schedule. Clinician involvement includes 6 hours of training and ongoing consultation plus 2 hours and 30 minutes of online surveys.

Project activities listed on Clinician Information Sheet will include:

- **A 3-hour interactive training** on measurement-based care in schools. This training will include how to collect, score, and use student- and parent-reported progress measures with students and families to improve engagement, personalize services and inform intervention planning and adjustments throughout the school year.
- **Six, 60-minute, monthly post-training consultation calls** for six months following the training. These calls will be with other participating clinicians and the PI to facilitate peer learning and support for implementing measurement-based care in

schools. Strategies and adaptations to match the school setting and student and family strengths and needs will be discussed.

- **Four, 30-minute online feedback surveys** from clinicians to understand measurement-based care acceptability, appropriateness, and feasibility in schools, plus clinician use of measures and related experiences with implementation. These will occur before the first training and 3 months, 6 months, and 9 months after the training throughout the school year. You will receive a \$25 Amazon gift card for each survey you complete.
- **Collecting student progress data.** You will be asked to collect brief measures of student progress periodically throughout treatment, review it with the student and family and document this in an online system that we will grant you access to called Better Outcomes Now (BON). Collecting and discussing these measures will take 5-10 minutes of session time, 2-4 times per month and will be part of the regular services you already provide. We ask that you do this with at least five (5) of your students.

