5.3 Statistical Method

5.3.1 Statistical Design

Quantitative Analyses

Quality control checks of the data and examination of variable distributions will be performed prior to formal analysis. There are *three* types of outcomes: (1) clinician report of acceptability, appropriateness, and feasibility (implementation outcomes), (2) clinician use of MBC (also an implementation outcome, fidelity), and (3) student engagement, progress and outcomes (effectiveness of MBC). For (1) and (2), the primary analysis will be a multilevel growth model with time (Level 1) nested within clinician (Level 2) for each of the implementation outcomes as they are clinician self-reported on clinician surveys. We will examine linear change of time as a continuous measure as well as time by time transitions across the longitudinal intervals of data collection. Attitudes toward MBC and other

independent variables (e.g., clinician professional and demographic characteristics, consultation call attendance, school district) will be entered into the models to examine correlations. In particular, we hypothesize parallel growth between attitudes and use of MBC over time.

For (3) we will conduct a 3-Level multilevel growth model with time (Level 1) nested within student/parent reported outcome (Level 1) nested within clinician (Level 3). Models will be estimated for each parent-reported outcome (e.g., parent-reported engagement, parent-reported symptoms on the PSC-35). Independent variables that will be entered as covariates in these models include MBC implementation outcomes, with the specific hypothesis that MBC use will be predictive of positive engagement and symptom reduction.

Also, for (3), the ORS and SRS are assessed at each session, hence, a mixed effects regression model will be used that accounts for intra-student correlation across student sessions and clustering of students within clinician. The unit of analysis will be session, however in primary analyses, to avoid an overly complicated model, session will not be modeled as a fixed effect in the regression model for the mean. Fixed effects will include time (baseline and post MP assessment for MP1, 2, or 3) and treatment condition (i.e. whether the clinician's agency is under the intervention or control condition).

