5.3.6 Handling of Missing Data

Missing data will be analyzed to examine any patterns of missingness not at random, including case-wise (i.e., overall percentage, patterns, various longitudinal intervals of missingness) and variable-wise (i.e., overall percentage, patterns) missing values analysis. Linear mixed modeling is robust to missing data and does not require listwise deletion of cases with missing data. Therefore, if missing data are missing at random (MAR) all data will be used. Otherwise, analyses with and without missing data will be compared to examine whether results differ when including cases and variables with data missing not at random.

6 Trial Administration

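### Survey reminders are triggered by not opening the link rather than by not submitting, so a clinician who opens a 30-minute survey and stops gets no reminder for that wave

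*Combined protocol and SAP*

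**What the plan says.** Section 5.3.3 Clinician Participants, step 5, states the only reminder rule for clinician surveys: "Two (2) reminders will be sent to clinicians who do not open the survey link". Step 4 of the same list places the information sheet and flyer on the first page of the online survey. The sentence after the reminder rule reads "All clinicians will receive emails about the 3 month, 6 month, and 9 month surveys regardless of baseline survey completion", and step 5 also allows for a clinician whose first completed survey is a follow-up.

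Section 5.2 Study Schedule describes "Four, 30-minute online feedback surveys", one before training and the others at 3, 6 and 9 months, with a $25 "Amazon gift card for each survey you complete".

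Section 4.2.1 collects the acceptability, appropriateness and feasibility measures (AIM, IAM, FIM) "via web-based, clinician-report survey". Section 5.1.1 (data source 1) adds self-reported use, measured by the CAPER, to the survey-based primary outcomes.

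Section 4.1.1 says "The primary comparison is pre-post ratings of implementation outcomes for all N=50 clinicians". Section 5.3.6 says "Linear mixed modeling is robust to missing data and does not require listwise deletion of cases with missing data".

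**The concern.** The event that stops reminders should be the event the study needs, which is a submitted survey. Here it is opening the link, and the protocol gives clinicians a reason to open it without answering, because the study information is on the first page. At 30 minutes a survey, opening it and setting it aside is also plausible.

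The study has no randomised comparator. The main contrast is each clinician against their own pre-training rating, so the baseline survey matters most. A missed 3- or 6-month survey is followed by another wave. A missed pre-training rating cannot be collected after training, and a missed 9-month rating has no later wave. At stake are some avoidable gaps in the survey-based primary outcomes, and a primary comparison that describes fewer than the 50 clinicians it names.

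**Working it through.** **Step 1. Who is reminded, read from 5.3.3 steps 4 and 5.**

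| Clinician's action at a wave | Reminders for that wave, as written | Later contact, as written |
|---|---|---|
| Does not open the link | Two | Emailed at each later wave |
| Opens, reads the first page, stops | None stated | Emailed at each later wave |
| Opens, answers part, stops | None stated | Emailed at each later wave |
| Submits | None needed | Emailed at each later wave |

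The second and third rows are the gap. No other section supplies a reminder for them. The text also leaves open whether the two reminders apply to the follow-up surveys. They follow the steps for the first survey, and for the later surveys only emails are mentioned.

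**Step 2. Which primary outcomes are exposed.** AIM, IAM, FIM and the CAPER come from the clinician survey. Fidelity is also a primary outcome, but the study team codes it from chart review or the Better Outcomes Now system (5.1.1, data source 2 and Table 1). Survey reminders do not affect it.

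**Step 3. What would be needed to size the loss.** Avoidable loss at a wave = 50 × (share who open and do not finish) × (share of those who would have finished if reminded). The documents give neither share. They also do not say whether partial responses are saved, whether the link can be reopened, or where the three 4-item measures sit in the survey. There is no stated power, detectable effect or dropout rate to reproduce.

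**Step 4. Illustration of scale.** Assume a simple paired pre-post mean, equal SDs at the two times and a pre-post correlation of 0.5. The SD of change is then √(2 × (1 − 0.5)) = 1 rating SD, and the 95% half-width is t(n−1) / √n.

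| Complete pairs | Clinicians without a pair | Half-width (SD) |
|---|---|---|
| 50 | 0 | 2.010 / √50 = 0.284 |
| 45 | 5 (10%) | 2.015 / √45 = 0.300 |
| 40 | 10 (20%) | 2.023 / √40 = 0.320 |
| 35 | 15 (30%) | 2.032 / √35 = 0.344 |

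Using 1.96 in place of t gives 0.277, 0.292, 0.310 and 0.331.

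**Step 5. Why these are upper-end figures.** They drop every clinician without a complete pair. The planned analysis is a multilevel growth model with time nested within clinician (5.3.1), over a baseline and three follow-ups. Under 5.3.6 it keeps clinicians with missing waves, so for a given number of missing surveys the loss of precision would be smaller. The 10% to 30% losses are assumed and are not tied to the reminder trigger.

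**The case against.** The strongest case against is that this is a small matter of wording. Every clinician is emailed at the next wave, each completed survey is paid, and monthly consultation calls keep clinicians in touch with the team. The analysis tolerates missing waves, and 5.3.6 also plans a missing-pattern analysis and a comparison of results if data are not missing at random. The study is a pilot, described in 3.1 as underpowered, with no precision target to miss. Someone who reads the information sheet and stops may have chosen not to respond, and 6.14 treats freedom from district influence as critical, so pursuing that person is partly a matter of judgement.

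Much of this stands, and it rules out several stronger readings that a reader might infer:

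- That partial starters are never contacted again. The sentence after the reminder rule contradicts this.
- That primary-outcome data are lost. The documents do not say that partial responses are discarded, and a partial response could already contain the key measures.
- That the missing clinicians would be the busier or less engaged ones. This is plausible, but nothing in the documents supports it.
- That the half-widths measure the effect of the trigger. They show only what a given number of lost pairs would do.
- That all primary outcomes are exposed. Coded fidelity is not.

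What the objection does not remove is the missing same-wave reminder. Later emails and the mixed model do not supply a clinician's own pre-training rating. Comparing analyses with and without the affected data recovers no observation. The point about non-response is met by excluding anyone who has declined.

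**Conclusion.** The concern holds in a limited form. As written, a clinician who opens a survey and stops gets no reminder for that wave. This may add avoidable missing data on AIM, IAM, FIM and self-reported use, above all at the pre-training baseline. The amount cannot be derived from the documents. In the complete-pair illustration, five lost pairs widen the 95% interval's half-width by 0.016 SD (0.300 − 0.284) and ten by 0.036 SD (0.320 − 0.284). Both rest on the assumed correlation of 0.5 and overstate the loss under the planned model. The point is a cheap improvement to conduct and does not undermine the analysis.

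**What to change.** In 5.3.3, step 5, change the trigger so that the two reminders go to clinicians who have not submitted the survey and have not declined. State that this applies at every wave, and that the baseline reminders are sent before the first training. The control period of at least one month in 4.1.1 leaves room for this. Add one sentence on how partly completed surveys are stored and used.

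Because every wave has to be listed, settle the survey count at the same time. The synopsis (Study Schedule) counts five surveys, including one post-training (5 × 30 = 150 minutes), while the list in 5.2 has four (4 × 30 = 120 minutes).

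The cost is a line or two of text, a survey-system setting and a few extra emails. Gift cards are paid per completed survey, so the team must already know who has finished.

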5.3 Statistical Method

5.3.1 Statistical Design

Quantitative Analyses

Quality control checks of the data and examination of variable distributions will be performed prior to formal analysis. There are *three* types of outcomes: (1) clinician report of acceptability, appropriateness, and feasibility (implementation outcomes), (2) clinician use of MBC (also an implementation outcome, fidelity), and (3) student engagement, progress and outcomes (effectiveness of MBC). For (1) and (2), the primary analysis will be a multilevel growth model with time (Level 1) nested within clinician (Level 2) for each of the implementation outcomes as they are clinician self-reported on clinician surveys. We will examine linear change of time as a continuous measure as well as time by time transitions across the longitudinal intervals of data collection. Attitudes toward MBC and other

independent variables (e.g., clinician professional and demographic characteristics, consultation call attendance, school district) will be entered into the models to examine correlations. In particular, we hypothesize parallel growth between attitudes and use of MBC over time.

For (3) we will conduct a 3-Level multilevel growth model with time (Level 1) nested within student/parent reported outcome (Level 1) nested within clinician (Level 3). Models will be estimated for each parent-reported outcome (e.g., parent-reported engagement, parent-reported symptoms on the PSC-35). Independent variables that will be entered as covariates in these models include MBC implementation outcomes, with the specific hypothesis that MBC use will be predictive of positive engagement and symptom reduction.

Also, for (3), the ORS and SRS are assessed at each session, hence, a mixed effects regression model will be used that accounts for intra-student correlation across student sessions and clustering of students within clinician. The unit of analysis will be session, however in primary analyses, to avoid an overly complicated model, session will not be modeled as a fixed effect in the regression model for the mean. Fixed effects will include time (baseline and post MP assessment for MP1, 2, or 3) and treatment condition (i.e. whether the clinician's agency is under the intervention or control condition).

Results of all the above analyses will be expressed in terms of 95% confidence intervals for effects and contrasts which together with estimates of intra-clinician correlation and variance will inform the power analysis for a larger trial.

Mixed Methods Analyses

For (2) we will also analyze chart review data. We will develop and test our MBC fidelity rubric on a subset of consented students at midpoint in the school year to assess intercoder reliability, test our coding form on the text of progress notes, and refine both our coding form and process for accessing records in an efficient, reliable manner. These analyses will yield mixed methods data on clinician use of MBC to be triangulated with clinician self-reported use of MBC on surveys to evaluate relative advantages and disadvantages of these methods to assess use of MBC. Qualitative data generated from chart reviews will be analyzed using Rapid Qualitative Analysis whereby two coders plus the PI will create summaries of chart review findings per student using a standard summary form, which is then entered into a matrix for the entire sample to be reviewed, coded iteratively, and synthesized for main themes and sub codes. These findings will directly inform the future R01 application methods regarding the collection and use of chart review and/or clinician surveys to assess MBC use/fidelity following implementation supports.

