Study Design

A clustered, multiple-baseline design will be used to examine the impact of implementation support on clinicians' fidelity, use and ratings of MBC appropriateness, acceptability and fidelity. Approximately 50 SMH clinicians will participate from up to three school districts as a part of their regular professional development activities. In these school districts, measurement based care implementation is a district-wide quality improvement initiative. All clinicians will receive the same implementation supports; there is no random assignment to condition. Following an initial control period of at least 1 month, school districts will start receiving implementation supports. Baseline MBC use, attitudes, acceptability, feasibility and appropriateness (per clinician self-report) will be collected, as well as needs assessment data from clinician surveys to inform necessary adjustments to the implementation supports. Baseline engagement and student outcomes will be collected after initial clinician training session. MBC implementation outcomes (i.e., MBC use, attitudes, acceptability, appropriateness, and feasibility), engagement and student outcomes will be collected at 3-month and 6-month follow-up during intervention supports, plus a 9-month follow-up interval. This allows clinicians in the school districts to be compared to each other and to their own baseline. The primary comparison is pre-post ratings of implementation outcomes for all N=50 clinicians. The secondary comparisons are pre-post ratings of engagement and student outcomes, and between-agency differences.

Clinicians will receive a 3-hour professional development on MBC in Fall 2022 that is required by the three participating school districts. Monthly, post-training group consultation calls will be conducted for 6-months, and online, self-report surveys will be collected at baseline, 3-month, 6-month and 9-month intervals. Clinicians will be asked to implement measurement-based care, using the Better Outcomes Now (BON) online feedback system, with at least 5 students each. Data in BON are deidentified and this activity is part of routine care provided by clinicians, so does not require special consent. These data will also be used to inform group consultation supporting clinicians' practices.

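### Does entering attitudes toward MBC into the clinician growth models distort the primary pre-post estimate?

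*Combined protocol and SAP*

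**What the plan says.** Section 4.1.1 (and the Synopsis, Study Design) names the target: "The primary comparison is pre-post ratings of implementation outcomes for all N=50 clinicians".

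Section 5.3.1 names the method: "For (1) and (2), the primary analysis will be a multilevel growth model with time (Level 1) nested within clinician (Level 2"), fitted for each implementation outcome. Its next sentence says how time will be examined: as a linear trend and as transitions between survey waves. A separate sentence then begins "Attitudes toward MBC and other", gives clinician characteristics, consultation-call attendance and school district as examples of the other independent variables, and says that these "will be entered into the models to examine correlations. In particular, we hypothesize parallel growth between attitudes and use of MBC over time".

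Attitudes are measured on both sides of the training. Section 4.1.1 says that in the control period "baseline MBC use, attitudes, acceptability, feasibility and appropriateness (per clinician self-report) will be collected". It and the Synopsis add that "MBC implementation outcomes (i.e., MBC use, attitudes, acceptability, appropriateness, and feasibility), engagement and student outcomes will be collected at 3-month and 6-month follow-up", with a further wave at 9 months. Table 1 puts the attitude scale in the clinician-survey block. Section 4.2.1 does not count attitudes as a primary outcome: "Implementation outcomes are selected from a published taxonomy of outcomes include acceptability, appropriateness, feasibility and fidelity".

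For the parent-reported outcomes, 5.3.1 uses different language: "Independent variables that will be entered as covariates in these models include MBC implementation outcomes". Section 5.3.4 likewise calls demographic variables controls when it adds them. Section 5.3.3 only points back to the statistical design section.

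**The concern.** The primary question is how much clinician ratings change from before to after the supports. Attitudes may change because of the same supports. Adjusting the time effect for a variable that moves after baseline takes out whatever part of the change runs alongside that variable, and leaves a different quantity. For MBC use, the plan itself expects attitudes to grow in parallel, so the adjusted effect would be too small.

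The sentence that adds attitudes refers to the models just described as primary. No sentence says that the pre-post estimate comes from a model without attitudes, or that only the baseline attitude score is used. Section 5.3.1 later sends the effects, their 95% confidence intervals and the variance estimates to the power analysis of a larger trial. An attenuated effect would distort that planning, which is a main purpose of the pilot.

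**Working it through.** **1. What the plan lets us reproduce.** Nothing numerical. Section 5.3.2 justifies 50 clinicians descriptively and gives no effect size, SD or power. The sizes below are illustrations on assumed inputs.

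**2. The identity.** Let T be the total pre-post change in the outcome, a the pre-post change in attitudes, and b the coefficient of outcome on attitudes given time. With attitudes as a time-varying covariate:

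adjusted time effect = T − b × a.

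Assume T = 0.50 SD. With outcome and attitudes both at unit variance and the same correlation between and within clinicians, b equals that correlation.

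| Attitude change a | b = 0.3 | b = 0.5 |
|---|---|---|
| +0.5 | 0.50 − 0.15 = 0.35 | 0.50 − 0.25 = 0.25 |
| +0.3 | 0.50 − 0.09 = 0.41 | 0.50 − 0.15 = 0.35 |
| 0 | 0.50 | 0.50 |
| −0.2 | 0.50 + 0.06 = 0.56 | 0.50 + 0.10 = 0.60 |

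If b is only 0.1 and attitudes rise 0.5, the effect is 0.50 − 0.05 = 0.45.

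**3. Interval coverage.** The simulation used 50 clinicians, four surveys, a within-clinician correlation over time of 0.5, a random-intercept model and the contrast of 6 months minus baseline. With attitudes up 0.5 SD, the 95% interval from the adjusted model contains the total change of 0.50 in about 82% (b = 0.3) or 49% (b = 0.5) of runs. With b = 0.1 it does so in 94%. With flat attitudes, coverage is 95–96%. The time-only interval has width 2 × 1.985 × √(2 × 0.5/50) = 0.56 SD and coverage of 94–96%.

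**4. Which specifications do harm.** The same simulation gives 0.50, with 94–96% coverage, when the model holds no attitudes, the baseline attitude score only, or each clinician's mean attitude. A variable that is constant within a clinician, entered as a main effect, cannot shift a within-clinician time contrast when data are complete. One attendance total per clinician is harmless for the same reason. A joint growth model with separate mean trajectories for attitudes and use also leaves the trajectory for use whole.

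Harm therefore needs four things together: time-varying entry, the headline effect read from that model, attitudes that move, and a material attitude-outcome link.

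**5. Whether the text adopts that model.** Three features of 5.3.1 point away from it.

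- *Order.* The primary analysis and the examination of change are described with time as the only named predictor. Attitudes arrive afterwards, in their own sentence.
- *Purpose.* That sentence gives association as the reason for entering attitudes. Where the plan means adjustment (the parent models in 5.3.1, the demographic variables in 5.3.4), it calls the variables covariates or controls. It does neither here.
- *Parallel growth.* This describes two processes changing together. It is hypothesised for use only. For acceptability, appropriateness and feasibility, the plan makes no statement that attitudes move with the outcome.

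**The case for a change.** The strongest case for a change is that the target is plainly total change, the growth models are plainly labelled primary, and attitudes are then put into those same models. The verb used for attitudes is the one used elsewhere for covariates. A sequential or joint reading is possible but never stated, so someone could choose the headline model after seeing the results. The effects and variances passed to the next trial are a main product of the pilot, and a sentence or two would settle the matter without new data.

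Part of this stands. The plan does not name the model that supplies the pre-post estimate, and the identity above is right for the specification it assumes. The rest is weaker. The shared verb is qualified by covariate or control language in the other two places and by a correlational purpose here, so the comparison favours the association reading. The provision on reporting covers all the analyses described, including the linear-change and transition analyses, and does not select an adjusted effect for the power analysis. Section 3.1 calls the pilot underpowered to establish outcomes with certainty, so no decision threshold turns on this coefficient. Consultation-call attendance would raise the same issue only if coded as an accumulating count, which the plan nowhere says.

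**Conclusion.** No change follows. Section 5.3.1 leaves a modelling step unstated, and the usual way of carrying it out (time-only growth model first, predictors or a joint model afterwards) follows the text and gives a sound pre-post estimate.

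The distortion under the contrary reading could be large: half of an assumed 0.50 SD change in the least favourable cell shown. It falls to nothing if attitudes are flat and to 0.05 SD if the link is weak (b = 0.1, attitudes up 0.5 SD). All of these sizes rest on assumed values for the true change, the attitude change, the correlations and complete data, and on a specification the plan does not adopt. The judgement would differ if the plan had called attitudes a time-varying adjustment variable, or had said that the primary time effect is read from the model containing them.
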